#### **7.2.2.2. Summaries of Treatment-Emergent Laboratory Abnormalities**

The following summaries (number and percentage of subjects) for treatment-emergent laboratory abnormalities will be provided by analyte and treatment group; subjects will be categorized according to the most severe postbaseline abnormality grade for a given analyte:

- Graded laboratory abnormalities
- Grade 3 or above laboratory abnormalities

For all summaries of laboratory abnormalities, the denominator is the number of subjects with nonmissing postbaseline values up to 30 days after the date of the last dose of study drug for the laboratory parameter of interest.

A by-subject listing of treatment-emergent Grade 3 or above laboratory abnormalities will be provided by subject ID number and visit in chronological order. This listing will include all test results that were collected throughout the study for the analyte of interest, with all applicable severity grades or abnormal flags displayed.

### **7.3. HIV RNA for HIV Coinfected Subjects**

The analysis of HIV RNA will be performed for HIV coinfecting subjects in Safety Analysis Set using data collected up to the date of the last dose of any study drug plus 30 days.

The proportion of subjects with HIV virologic rebound during the study will be summarized. Subjects with HIV virologic rebound are defined as those with HIV RNA  $\geq 400$  copies/mL at at least 2 consecutive postbaseline on-treatment visits which are at least 2 weeks apart based on actual dates.

By-subject listings of HIV virologic rebound will be provided and include HIV RNA, CD4 counts (absolute and percentage), HCV RNA, HIV current antiretroviral medication, and HCV treatment during the study.

A contingency table of the number of subjects with HIV RNA < 400 or  $\geq$  400 copies/mL at baseline and postbaseline visits by CD4 count < 200 cells/ $\mu$ L or  $\geq$  200 cells/ $\mu$ L at baseline will be generated. The number and proportion of subjects with HIV RNA < 50 or  $\geq$  50 copies/mL will be summarized by visit. Median (Q1, Q3) and mean ( $\pm$  SD) change from baseline in HIV RNA (copies/mL) will be summarized and plotted by visit for subjects with detectable HIV RNA at baseline. A listing of subjects with HIV RNA  $\geq$  50 copies/mL will be provided.

The denominator for proportion of subjects with HIV rebound, the contingency table of HIV RNA by CD4 counts, and the proportion of subjects with HIV RNA < 50 or  $\geq$  50 copies/mL will be the number of subjects in the Safety Analysis Set with HIV coinfection.

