3.3.2. HIV Virologic Rebound Criteria

[figure not shown]
Subjects who have at least two consecutive post-baseline visit plasma HIV-1 RNA levels ≥ 400 copies/mL (at least two weeks apart) will be considered to have HIV virologic rebound.

Following an initial HIV-1 RNA result of ≥ 400 copies/mL, subjects will continue to take their current ARV regimen and be asked to return to the clinic after 2 weeks for a scheduled or unscheduled blood draw for confirmation of HIV virologic rebound. If HIV virologic rebound is confirmed at the scheduled or unscheduled visit, the blood samples from this visit will be used for HIV-1 genotype/phenotype testing. If no resistance to the subject's current ARV regimen is detected, the subject may continue on current ARV regimen. If resistance to the subject's current ARV regimen is detected, then it is strongly recommended that whenever possible, the subject be switched to an alternative approved regimen, as outlined in Section 4.2 of this protocol.

HCV study drug should be continued unless safety events warrant the discontinuation of the study drug, as outlined in Section 3.5 of the protocol, or if a subject must be switched to an unapproved HIV regimen based upon acquired resistance.

Please refer to [Figure 3-1](#) for the management of subjects who meet the criteria for HIV virologic rebound.

Figure 3-1. HIV Virologic Rebound Schema

- a HCV study drug should be continued unless safety events warrant the discontinuation of these study drugs, as outlined in Section 3.5 of the protocol
- b If virologic rebound is not confirmed, the subject should remain on their current ARV regimen.
- c If virologic rebound is confirmed, the HIV-1 genotype and phenotype (reverse transcriptase and protease) will be analyzed.
- d Based on the results of the genotype and phenotype assays, the subject may remain on their ARV regimen at the discretion of the Investigator (e.g. virologic rebound due to non-adherence). If the genotype and/or phenotype assay fails to provide results, a new ARV regimen may be configured at the discretion of the Investigator in consultation with the Medical Monitor.

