6.3.5. Unscheduled Visit

A subject should attend an unscheduled visit if requested by the sponsor or the investigator. The assessments are at the investigator's discretion. At all unscheduled visits initiated for the purpose of confirming HCV or HIV virologic failure, a sample for HCV RNA Sequencing / Phenotyping, or a sample for HIV RNA Genotyping/Phenotyping, respectively, must be collected.

The Sponsor (e.g. Medical Monitor and Clinical Trial Manager) and CRO must be informed, as soon as possible, when a subject comes off treatment due to an AE.

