#### **3.8.2. Analysis Visit Windows**

Subject visits may not occur on protocol-specified days. Therefore, for the purpose of analysis, observations will be assigned to analysis windows.

In general, the baseline value will be the last nonmissing value on or prior to the date of the first dose of study drug.

HCV RNA, vital signs, safety laboratory data, HIV-1 RNA and CD4 counts (HIV-1 RNA and CD4 counts will be assessed for subjects with HIV coinfection only) collected up to the date of the last dose of study drug plus 3 days will be considered to be on-treatment data; HCV RNA, vital signs, safety laboratory data, and HIV-1 RNA and CD4 counts collected after the date of the last dose of study drug plus 3 days will be considered posttreatment data. The analysis windows for on-treatment HCV RNA, vital signs, safety laboratory data, and HIV-1 RNA and CD4 counts are provided in [Table 3-1](#).

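### SAP 7.3 needs both HIV rebound values on treatment, so a rebound first seen at a compliant Week 12 visit and confirmed later is left out of the rebound proportion

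*SAP*

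**What the plan says.** Protocol 3.3.2 sets the rebound criterion as "Subjects who have at least two consecutive post-baseline visit plasma HIV-1 RNA levels" of 400 copies/mL or more, at least two weeks apart. Neither value has to be on study treatment. After a first high value the subject will "be asked to return to the clinic after 2 weeks for a scheduled or unscheduled blood draw for confirmation of HIV virologic rebound". Protocol 6.3.5 expects such visits: "At all unscheduled visits initiated for the purpose of confirming HCV or HIV virologic failure", a resistance sample must be taken. HIV-1 RNA is also scheduled for coinfected subjects at post-treatment Weeks 4 and 12 (protocol 6.4.1, 6.4.2 and Appendix 2).

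SAP 7.3 opens with a broad label, "The proportion of subjects with HIV virologic rebound during the study will be summarized", and the section works "using data collected up to the date of the last dose of any study drug plus 30 days". Its definition is narrower: at least 400 copies/mL at no fewer than "2 consecutive postbaseline on-treatment visits which are at least 2 weeks apart based on actual dates". The denominator "will be the number of subjects in the Safety Analysis Set with HIV coinfection". SAP 3.8.2 fixes what on-treatment means for HIV-1 RNA: values "collected up to the date of the last dose of study drug plus 3 days will be considered to be on-treatment data".

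For HCV breakthrough and rebound, SAP 6.2.1 expressly lets the second, confirming value fall after treatment. SAP 7.3 has no such allowance.

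**The concern.** A two-week confirmation interval combined with a three-day on-treatment tail leaves a blind spot at the end of treatment. Suppose a coinfected subject first reaches 400 copies/mL at Week 12, returns two weeks later as the protocol asks, and is still high. The protocol calls this rebound. The SAP scores it as no rebound and keeps the subject in the denominator.

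The error runs one way: the rule can drop a confirmed rebound but cannot add a false one. What is at stake is whether Table 15.11.6.2.1 and Listing 16.2.8.1.10, whose title refers to the study rather than to treatment, report what a reader will take them to report.

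**Working it through.** The plan gives no figure for this output, so there is none to reproduce. The check is day arithmetic.

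**Inputs**
- Minimum gap between the two values: 14 days (SAP 7.3).
- On-treatment limit: last dose day L plus 3 (SAP 3.8.2).
- Planned dosing: 12 weeks, so L = 84. L = 81 and L = 87 are also tested.
- Visits, each ±3 days (protocol 6.3.2 to 6.3.4): Week 2 = days 11–17, Week 4 = days 25–31, Week 8 = days 53–59, Week 12 = days 81–87. Study drug is returned at Week 12.
- Post-treatment Week 4, ±5 days from 28 (protocol 6.4.1): FU days 23–33, where FU day = date minus L.
- Data span of SAP 7.3: L + 30.

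**1. Latest first value X that can be counted.** X + 14 ≤ L + 3, so X ≤ L − 11. This gives day 70, 73 or 76 for L = 81, 84 or 87.

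**2. Which visits qualify.** The latest compliant Week 8 day is 59, below 70, so every Week 2, 4 and 8 visit day can be confirmed on treatment. The earliest Week 12 day is 81, above 76, so no Week 12 visit day can.

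**3. How long dosing would have to run.** L ≥ X + 11: day 92 for a day 81 visit, day 95 for day 84 and day 98 for day 87.

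**4. Where the confirming draw falls.** Earliest confirmation is X + 14 = days 95–101.
- With L = 84 this is FU day 11–17.
- With L anywhere from the visit day to day 87, it runs from 81 + 14 − 87 = FU day 8 up to FU day 14 (when L = X).
- Together the range is FU day 8–17: always past the 3-day limit, always within 30 days.

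**5. The scheduled post-treatment Week 4 visit as confirmation.** Over the same combinations, the shortest gap from Week 12 is 84 + 23 − 87 = 20 days and the longest is 87 + 33 − 81 = 39 days, so the two-week gap is always met. Of its 11 permitted days, FU 23–30 (8 days) lie inside the 30-day span and FU 31–33 (3 days) do not.

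**6. What is still counted.** A subject high at Week 8 and again at Week 12 has a gap of 81 − 59 = 22 to 87 − 53 = 34 days and is counted. So is a subject with an earlier unscheduled high draw, for example on days 71–73 confirmed by day 87 when L = 84. Only a rebound whose first high value is the Week 12 value is lost.

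**7. Size.** Each missed subject lowers the proportion by 1/n. The documents give neither the coinfected n nor a rebound rate. On assumed values, one subject is 10 percentage points at n = 10 and 2.5 at n = 40.

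**The case against.** The strongest reply is that this is a permitted design choice. Protocol 3.3.2 serves subject management. The rebound proportion is not among the endpoints in protocol 9.1. Protocol 9.6.5 ties its own HIV measure, staying below 50 copies/mL, to the HCV treatment period and leaves the detail to the SAP. That stands. A reader might infer that SAP 7.3 is an undeclared deviation, given that SAP 7.8 declares none; the documents do not support that, because the protocol delegates this analysis. What survives is narrower: the first value is on treatment, only its confirmation is not, and the section's own label and data span cover that confirmation.

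A reader might also infer that the signal is hidden. It is not. SAP Table 3-2 assigns HIV-1 RNA on FU days 4–30 to the FU-4 visit, so both values can appear in the by-visit summaries and the HIV RNA by CD4 table, and Listings 16.2.8.1.11 and 16.2.8.1.12 can show them. A careful reader could find the subject, but the headline proportion would still omit that subject.

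Finally, one might argue for counting all post-baseline values through post-treatment Week 12 so as to reproduce protocol 3.3.2. That would exceed the 30-day safety span in protocol 9.6 and require changes to Table 3-2, where FU-12 is not applicable for HIV-1 RNA. It would also move the same unconfirmable edge to the last study visit, so it would not fully match the protocol either.

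**Conclusion.** The point holds as a minor one, worth considering. With 12-week dosing and a compliant Week 12 visit, a first value of at least 400 copies/mL at that visit cannot be counted as rebound under SAP 7.3, although once confirmed it meets protocol 3.3.2. One of the four scheduled on-treatment HIV RNA visits therefore cannot supply a countable first value. The bias has a known direction (understatement) and an unknown size.

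It would be too strong to say that a high Week 12 value never counts. The exceptions are dosing to about day 92 or later and an earlier unscheduled high draw, and a subject already high at Week 8 is counted. The output is descriptive and confined to a coinfected subset of unstated size, whose entry criteria require suppressed HIV RNA on stable therapy. Primary efficacy and adverse event analyses are unaffected.

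**What to change.** In SAP 7.3, state that when the first value of at least 400 copies/mL is on treatment, the confirming value, at least 2 weeks later, may be post-treatment provided it falls within the existing last dose plus 30 days. SAP 6.2.1 is the model. Label Table 15.11.6.2.1 and Listing 16.2.8.1.10 as HIV rebound with onset on treatment. Add a note that rebound first seen after treatment is not counted, and that a confirming value after FU day 30 appears only in the listings.

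The cost is one or two sentences, two titles and a footnote. No new data are collected and the 30-day span is unchanged. One gap remains: a Week 12 rebound confirmed only by a post-treatment Week 4 draw on FU days 31–33 stays uncounted. Closing it would mean going past the 30-day span used in SAP 7.3, Table 3-2 and protocol 9.6, which this point does not justify.

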9.6.5. HIV RNA Analysis

Subjects with HCV/HIV co-infection RNA < 50 copies/mL at Baseline/Day 1 will be summarized by visit to assess the proportion of subjects that maintain HIV-1 RNA < 50 copies/mL while on HCV treatment.

Details on HIV-1 RNA related safety analyses will be described in the statistical analysis plan.

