### 3.6. Missing Data and Outliers

#### 3.6.1. Missing Data

In general, missing data will not be imputed unless imputation methods for handling missing data are specified.

For missing last dosing date of a study drug, imputation rules are described in Section 3.8.1. The handling of missing or incomplete dates for adverse event (AE) onset is described in Section 7.1.5.2 and for prior and concomitant medications in Section 7.5.

For analyses of categorical HCV RNA data, missing posttreatment HCV RNA data will have the missing data imputed. Missing on-treatment HCV RNA will have missing data imputed up to the date of the last dose (for on-treatment displays). If the study day associated with the last dosing date of any study drug is greater than or equal to the lower bound of a visit window, and the value at the visit is missing, then the value will be imputed. If the study day associated with the last dosing date is less than the lower bound of a visit window then the on-treatment value at that visit will remain missing.

If an HCV RNA data point is missing and is preceded and followed in time by values that are “< LLOQ target not detected (TND),” then the missing data point will be set to “< LLOQ TND.” If a data point is missing and preceded and followed by values that are “< LLOQ detected,” or preceded by “< LLOQ detected” and followed by “< LLOQ TND,” or preceded by “< LLOQ TND” and followed by “< LLOQ detected,” then the missing value will be set to “< LLOQ detected.” In these situations the data point will be termed a bracketed success; otherwise, the data point will be termed a bracketed failure (ie,  $\geq$  LLOQ detected). If a data point is missing and is not bracketed, the missing data point will also be termed a failure (ie,  $\geq$  LLOQ detected).

For the analyses of continuous HCV RNA efficacy data, when and only when a missing HCV RNA value is imputed as “< LLOQ TND” or “< LLOQ detected” according to the imputation rule described above, the corresponding continuous value will be imputed to LLOQ – 1 IU/mL (ie, HCV RNA 14 IU/mL). No other imputation will be performed for continuous HCV RNA data.

For the analyses of continuous HIV RNA data, for subjects with a missing HIV RNA value in a visit window that is bracketed by prior and subsequent values, the numerical value of HIV RNA will be imputed using the larger value. No other imputation will be performed for HIV RNA data.

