**Table 3-2. Analysis Windows for Posttreatment HCV RNA, Vital Signs and Safety Laboratory Data, HIV-1 RNA and CD4 Counts**

Nominal FU a Visit	HCV RNA			Vital Signs, HIV-1 RNA, CD4 Counts and Other Safety Laboratory Data b		
	Nominal FU Day	Lower Limit	Upper Limit	Nominal FU Day	Lower Limit	Upper Limit
FU-4	28	21	69	28	4	30
FU-12	84	70	146	NA	NA	NA

a FU-x visit = posttreatment Week-x follow-up visit.

b Posttreatment vital signs, safety labs, HIV-1 RNA, and CD4 counts will be summarized only for the FU-4 visit (ie, up to 30 days after last dose).

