#### **7.8. Changes From Protocol-Specified Safety Analyses**

There are no deviations from the protocol-specified safety analyses.

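### The SAP's by-visit HIV suppression summary divides by all co-infected subjects, not by those suppressed at baseline as the protocol specifies, and gives missing values no category

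*SAP*

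**What the plan says.** Protocol 9.6.5 sets both the population and the measure: "Subjects with HCV/HIV co-infection RNA < 50 copies/mL at Baseline/Day 1 will be summarized by visit", with the aim of finding the proportion who "maintain HIV-1 RNA < 50 copies/mL while on HCV treatment". It leaves further details of the HIV-1 RNA safety analyses to the SAP.

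SAP 7.3 plans a count and proportion below 50 and at or above 50 copies/mL by visit (Table 15.11.6.2.4). One sentence sets the denominator for this table, for the rebound proportion and for the contingency table of HIV RNA by CD4 count: it "will be the number of subjects in the Safety Analysis Set with HIV coinfection". No baseline condition is attached.

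On missing data, SAP 3.6.1 has one rule for HIV RNA. It opens "For the analyses of continuous HIV RNA data, for subjects with a missing HIV RNA value in a visit window" and assigns a bracketed gap the larger of the two neighbouring values. Nothing else is imputed. SAP 7.3 gives no missing category for the <50/≥50 table.

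SAP 7.3 also summarises and plots change from baseline in HIV RNA "for subjects with detectable HIV RNA at baseline".

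SAP 7.8 then states: "There are no deviations from the protocol-specified safety analyses".

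**The concern.** Maintaining suppression is defined only for a subject who was suppressed at the start. The SAP's denominator includes anyone co-infected, so its percentage does not estimate the protocol's measure whenever someone enters treatment at or above 50 copies/mL. The documents foresee such subjects. Inclusion criterion 13 tolerates isolated or unconfirmed values above 50. The exclusion of HIV RNA above 50 applies at screening, up to 28 days (42 if extended) before Day 1. SAP 5.2 plans a baseline category of 50 copies/mL or more.

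The second problem is separate. A subject with no usable value at a visit stays in the denominator but enters neither row, so the two percentages need not add to 100 and the shortfall is unexplained. SAP 7.2.2.2 uses subjects with non-missing postbaseline values as the denominator for other laboratory abnormalities, so the HIV table departs from the SAP's own convention without a stated reason.

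At stake is how readable the summary is as a check that HCV treatment does not disturb HIV control. SAP 7.8 also tells the reader that nothing has changed from the protocol.

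**Working it through.** The plan states no figure for this summary, so there is nothing to reproduce. The population mismatch follows from setting Protocol 9.6.5 beside SAP 7.3. The arithmetic below shows direction and possible size only.

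**Notation.** N co-infected subjects, of whom S are below 50 copies/mL at baseline and U are not (N = S + U). At a given visit, a of the S and b of the U are at ≥50, and m of the S have an unbracketed missing value.

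- SAP ≥50 rate: (a + b)/N
- Baseline-suppressed subjects, fixed denominator: a/S
- Baseline-suppressed subjects with a value: a/(S − m)

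The SAP rate exceeds a/S exactly when b/U > a/S, that is, when unsuppressed subjects stay at ≥50 more often than suppressed subjects reach it.

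**Assumed inputs.** The documents give no number co-infected, number unsuppressed at baseline or missing rate. I take N = 20 or 40, U = 0 or 2, a = 2, and about 20% of S missing.

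| N | U | b | m | SAP (a+b)/N | Suppressed, fixed a/S | Suppressed, observed a/(S−m) |
|---|---|---|---|---|---|---|
| 20 | 0 | 0 | 4 | 2/20 = 10.0% | 2/20 = 10.0% | 2/16 = 12.5% |
| 20 | 2 | 0 | 4 | 2/20 = 10.0% | 2/18 = 11.1% | 2/14 = 14.3% |
| 20 | 2 | 2 | 4 | 4/20 = 20.0% | 2/18 = 11.1% | 2/14 = 14.3% |
| 40 | 0 | 0 | 8 | 2/40 = 5.0% | 2/40 = 5.0% | 2/32 = 6.25% |
| 40 | 2 | 2 | 8 | 4/40 = 10.0% | 2/38 = 5.3% | 2/30 = 6.7% |

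For the <50 row in the first case, the SAP gives (20 − 2 − 4)/20 = 14/20 = 70.0%. Among subjects with a value it is 14/16 = 87.5%.

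**Reading the table.**

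1. With U = 0 the two populations coincide, yet the SAP figures still differ from observed cases. That gap comes wholly from the fixed denominator. Restricting to baseline-suppressed subjects would not remove it (10.0% in both fixed columns).
2. With U = 2, the SAP's ≥50 rate falls below or rises above both protocol-population figures, depending on b.
3. Missing values pull the <50 and ≥50 percentages down together.

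If the bracketing rule does not reach this categorical table, bracketed gaps also fall in neither row. The SAP does not say.

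**The case against.** The case for leaving the plan alone has real weight. Protocol 9.6.5 delegates details to the SAP. Entry requires maintained HIV RNA below 50 and screening excludes values above 50, so few subjects should be unsuppressed on Day 1. The SAP reports counts as well as percentages, a rebound table, a listing of subjects at ≥50, and a full listing of HIV RNA and CD4. In a small subgroup each loss of suppression will be visible. A fixed denominator also makes the maintained percentage lower, which is the cautious direction for the protocol's stated measure. The protocol does not prescribe an observed-case denominator.

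Most of this stands and limits the size of the point. It does not dispose of it: the population in which maintenance is assessed is part of the protocol's specification, and SAP 7.8 says nothing has changed.

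Three stronger readings are tempting and are not supported:

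- A reader might infer that the SAP understates loss of HIV control. Against observed cases it does when all are suppressed at baseline. In general the direction is open, as the 20.0% against 14.3% case shows.
- A reader might infer that the change-from-baseline summary is biased toward a decrease because it omits suppressed subjects. SAP 3.7 and Protocol 9.3 distinguish no HIV RNA detected from detected below 20 copies/mL, so detectable subjects can include those below 20 and those at 20–49, who are suppressed by the 50-copy rule. Results detected below 20 are set to 19, the floor, and can only stay level or rise. Table 15.11.6.2.3 is also listed for all co-infected subjects; only the two figures carry the restriction in their titles. What remains is an inconsistency between the SAP 7.3 text and that table.
- A reader might add that a post-treatment Week 4 visit on days 31–33, allowed by the ±5-day window, falls past the SAP's day-30 limit. That is so, but the protocol's measure concerns the time on HCV treatment, and the 30-day limit is the protocol's own safety rule (section 9.6).

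**Conclusion.** The point holds as a minor correction. SAP 7.3 uses a different population from Protocol 9.6.5 and SAP 7.8 does not declare it. This is established by reading alone. Including subjects unsuppressed at baseline can move the ≥50 percentage either way. Separately, the fixed denominator without a missing category lowers both percentages relative to observed cases: 10.0% against 12.5% for ≥50 and 70.0% against 87.5% for <50, with 20 co-infected, all suppressed at baseline, 4 missing and 2 at ≥50. Those counts are assumed. The real effect is probably small, given the screening exclusion and the by-subject listing. Nothing here touches the primary SVR12 analysis, and the documents do not support a claim that the plan hides loss of HIV control.

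**What to change.** In SAP 7.3 and Table 15.11.6.2.4:

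- Restrict the <50/≥50 by-visit summary to co-infected subjects with baseline HIV RNA below 50 copies/mL. The denominators for rebound and for the CD4 contingency table need not change.
- Show the number below 50, at or above 50, and missing at each visit, with the percentage taken among subjects with a value.
- State whether the larger-value rule for bracketed gaps applies to this table.
- Align the detectable-at-baseline restriction in the 7.3 text with the unrestricted Table 15.11.6.2.3, so that change is tabulated for all co-infected subjects.
- Record in SAP 7.8 any difference from Protocol 9.6.5 that remains.

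The cost is SAP wording and a little table programming, with no new data. One drawback is that the maintained percentage among subjects with a value is less conservative than the fixed-denominator one. The missing row makes that visible.
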